Randomization of the study participants is carried out on the same day or the next day after signing the informed consent, but no later than 3 days from the date of material sampling to the PCR test.

Randomization is carried out according to the Randomization List version 1.00 from 16.11.2020. To randomize a participant into a study, a research physician must contact the employee responsible for randomization (instructions for randomization are provided by the sponsor to the center before the start of the study) by phone and provide the study code and the researcher's full name for identification, as well as the data of the randomized participant: screening number, initials, date of birth. The researcher is informed of the assigned randomization number of the participant and the number of the prevention group (I or II). After the call, a Randomization Form is sent to the researcher's email as confirmation. The form must be printed out, signed by the researcher, and attached to the primary documentation of the participant.

The intake of the study drug is carried out independently by the participant at home, with the Diary of the participant of the study.

Other preventive measures

Any non-specific measures for the prevention of a new coronavirus infection COVID-19 are allowed, including personal protective equipment (respirators, glasses, gloves, protective suits).

Previous therapy

As a previous therapy, it is prohibited to take any drug with test status 1 month before participating in this study.

Concomitant therapy

According to the design of the non-interventional study, participants can receive any concomitant therapy for concomitant chronic diseases, except medications prescribed off-label or for research purposes.

Prohibited therapy

For the study group: use of any medications that may or may have preventive effects against ARVI, including COVID-19, is **prohibited**; use of non-specific methods of preventive protection is **not prohibited**.

For the control group: use of interferon gamma is **prohibited**; use of any medications that may or may have preventive effects against ARVI, including COVID-19, as well as the use of non-specific methods of preventive protection is **not prohibited**.

All preventive measures, including pharmacotherapeutic ones, should be indicated in the diary filled in by the participant.

Exclusion criteria

A participant should be excluded from the study if at least one of the following criteria is met:

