1. The use of the prohibited therapy indicated above, specific to each of the groups.
2. Withdrawal of informed consent.
3. Compliance to the study therapy is 50% or less.
4. Systematic non-compliance with protocol procedures by the participant.
5. Development of individual intolerance to the study drug (for the study group).
6. The development of concomitant diseases or conditions that, according to the researcher, may distort the results of the study, restrict the rights of the volunteer or put him at greater risk.
7. The appearance of contraindications to the use of the study drug in the period before the last intake of the second 10-day cycle (for the study group).
8. Participation in a clinical trial using a different therapy.
9. Disagreement on following reliable contraceptive measures (sexual abstinence; or a combination of 2 different methods: for example, barrier and spermicides, or barrier and intrauterine device, or barrier and hormonal, etc.) – for participants with preserved childbearing potential in the period before the last intake of the second 10-day cycle (for the study group).
10. Pregnancy.

A woman who excluded from the study due to the onset of pregnancy during the clinical trial is subject to medical supervision during the entire period of pregnancy, as well as for 6 months postpartum period to assess the condition of the woman and the born child (observation is carried out if possible and only if her desire and consent to such observation is mandatory). Information about the course of pregnancy and its outcome is entered in the primary documentation (with the consent of the woman). During the entire period of pregnancy, together with an obstetrician-gynecologist (with the consent of the pregnant woman and, if possible, contact with a doctor), observing a woman, her general condition, data reflecting the nature of the course of pregnancy, results of laboratory and instrumental examination methods, including ultrasound, are analyzed. Monitoring of the born child is carried out with the consent of the woman together with the district pediatrician (if possible, contact with him) until the child is 6 months old to analyze the clinical status of the child, data from laboratory and instrumental research methods.

There are no procedures for replacing excluded participants.

Diaries of participants

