|---------------------------------|---|

Administration of study drug

Time of administration: | ____ :| ____ |

In case of complaints, symptoms of ARVI, please fill out the table below:

| Start date | End date | Complaints | Therapy (if taken) |
|------------|----------|------------|--------------------|
| | | | |
| | | | |
| | | | |
| | | | |

| | |
|---------------------------------|--|
| Course 1 Day 2 | Date ____ ____ ____ ____ ____ day month year |
|---------------------------------|--|

In case of complaints, symptoms of ARVI, please fill out the table below:

| Start date | End date | Complaints | Therapy (if taken) |
|------------|----------|------------|--------------------|
| | | | |
| | | | |
| | | | |
| | | | |

| | |
|---------------------------------|--|
| Course 1 Day 3 | Date ____ ____ ____ ____ ____ day month year |
|---------------------------------|--|

Time of administration: | ____ :| ____ |

In case of complaints, symptoms of ARVI, please fill out the table below:

| Start date | End date | Complaints | Therapy (if taken) |
|------------|----------|------------|--------------------|
| | | | |
| | | | |
| | | | |
| | | | |

| | |
|---------------------------------|--|
| Course 1 Day 4 | Date ____ ____ ____ ____ ____ day month year |
|---------------------------------|--|

In case of complaints, symptoms of ARVI, please fill out the table below:

| Start date | End date | Complaints | Therapy (if taken) |
|------------|----------|------------|--------------------|
| | | | |
| | | | |
| | | | |
| | | | |

| | |
|---------------------------------|--|
| Course 1 Day 5 | Date ____ ____ ____ ____ ____ day month year |
|---------------------------------|--|

Time of administration: | ____ :| ____ |

In case of complaints, symptoms of ARVI, please fill out the table below:

| Start date | End date | Complaints | Therapy (if taken) |
|------------|----------|------------|--------------------|
| | | | |
| | | | |
| | | | |
| | | | |

| | |
|-----------------|--|
| Course 1 | Date ____ ____ ____ ____ ____ |
|-----------------|--|

| | |
|--------------|----------------|
| Day 6 | day month year |
|--------------|----------------|

In case of complaints, symptoms of ARVI, please fill out the table below:

| Start date | End date | Complaints | Therapy (if taken) |
|------------|----------|------------|--------------------|
| | | | |
| | | | |
| | | | |

| | |
|---------------------------------|--|

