Research participant's diary

Protocol of post-marketing non-interventional study

"A prospective randomized open-label comparative study of the use of the intranasal form of human recombinant interferon gamma for the prevention of acute respiratory viral infections, including diseases caused by coronavirus infection 2019 (COVID-19)"

RAIN-2020

Control Group

Participant screening number: |__|_|__|_|__|_|

Randomization number of the participant: |__|_|__|_|__|_|

Date of signing informed consent: |__|_|__|_|__|_|__|_|__|_|

day month year

The start date for the diary: |__|_|__|_|__|_|__|_|__|_|
day month year

The end date for the diary: |__|_|__|_|__|_|__|_|
day month year

Participant's signature _____

Signature of the medical researcher _____

| Participant _____ (randomization number) | Initial data | Date __ _ __ _ __ _ day month year |
|---|--------------|---|
|---|--------------|---|

| | | |
|---------------------|------------------------------------|----|
| 1. Initials | | |
| 2. Date of birth | | |
| 3. Gender | male / female | |
| 4. Smoking, history | yes (____ pack/day for ____ years) | no |

The observation period is 2 months

If you are taking medications to prevent ARVI, please fill out the table below:

| | |
|---|---------------------------|
| Participant _____ (randomization number) | Observation period |
| Participant _____ (randomization number) | Observation period |

In case of complaints, symptoms of ARVI, please fill out the table below:

¹⁶ Before using the drug, it is necessary to familiarize yourself with the current instructions for medical use to exclude contraindications.

¹⁷ A single dose and the frequency of dosing are indicated

| | | | |
|--|--|--|--|
| | | | |
| | | | |
| | | | |
| | | | |
| | | | |
| | | | |
| | | | |

Appendix 3

Form for reporting unlabeled serious adverse reaction

Reporting of unlabeled serious reaction to a drug being studied in a clinical trial

| | | | | | |
|---|--|--|--|--|--|
| Research protocol No. | | | | | |
| Name of the research protocol | | | | | |
| Name of study drug | | | | | |
| Study phase | | | | | |
| The name of the medical institution in which the SAE was detected | | | | | |

Information about the SAE

| | | | | | |
|--|------------------|--------|-----------|--------------------------|--|
| 1. Initials of the patient | 2. Date of birth | 3. Age | 4. Gender | 5. Start date of the SAE | 6. Mark everything that corresponds to the SAE |

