6. TABLE PATTERNS

Table1. Distribution of subjects

Distribution of subjects	Group I (proportion, %)	Group II (proportion, %)
Included in the study (screened)	n/N (%)	
Of these:		
Excluded at the screening stage:	n/N (%)	
Randomized	n/N (%)	n/N (%)
Prematurely excluded, out of them:	n/N (%)	n/N (%)
Existence of exclusion criterion #X (description)	n/N (%)	n/N (%)
Population safety	n/N (%)	n/N (%)
ITT population	n/N (%)	n/N (%)
Population PP	n/N (%)	n/N (%)

Table2. Demographic and anthropometric characteristics of subjects at the time of inclusion (safety population)

Group	Parameter	Age (years)	Weight (kg)	Height (cm)	Smoking index (p/y)	Frequency of acute respiratory infections (amount/g)
GROUP I	n					
	M					
	CO					
	min.					
	max.					
	Me					
GROUP II	n					
	M					
	CO					
	min.					
	max.					
	Me					
p (between groups)						

Table3. Distribution of subjects by gender (safety population)

Gender	GROUP I	GROUP II
Male	n/N (%)	n/N (%)
Female	n/N (%)	n/N (%)
p (between groups)		

Table4. Distribution of subjects by race (safety population)

Race	GROUP I	GROUP II
Caucasian	n/N (%)	n/N (%)
Mongoloid	n/N (%)	n/N (%)
Negroid	n/N (%)	n/N (%)
p (between groups)		

Table5. Medical history (safety population)

Parameter	Value	Group I (N =)	Group II (N =)
Diagnosis (chronic disease)	...	n/N (%)	n/N (%)
Diagnosis (according to anamnesis)	...	n/N (%)	n/N (%)
p (between groups)			

Table 6. Methods of nonspecific prevention (safety population)

Type	Frequency	GROUP I	GROUP II
Total subjects		N =	N =
Masks	Yes	n/N (%)	n/N (%)
	No	n/N (%)	n/N (%)
	Sometimes	n/N (%)	n/N (%)
Respirator	Yes	n/N (%)	n/N (%)
	No	n/N (%)	n/N (%)
	Sometimes	n/N (%)	n/N (%)
Gloves	Yes	n/N (%)	n/N (%)
	No	n/N (%)	n/N (%)
	Sometimes	n/N (%)	n/N (%)
Glasses	Yes	n/N (%)	n/N (%)
	No	n/N (%)	n/N (%)
	Sometimes	n/N (%)	n/N (%)
Surgical overalls	Yes	n/N (%)	n/N (%)
	No	n/N (%)	n/N (%)
	Sometimes	n/N (%)	n/N (%)
p (between groups)			

Table 7. Drug allergy (safety population)

	GROUP I	GROUP II
Total subjects	N =	N =
No	n/N (%)	n/N (%)
Yes	n/N (%)	n/N (%)
p (between groups)		

Table 8. Results of the assessment of the incidence rate at the end of the prevention period (ITT/PP/ITT_NV/PP_NV/ITT_NV_BE/PP_NV_BE population)

	GROUP I	GROUP II
Total subjects	N =	N =
ARVI	n/N (%)	n/N (%)
Not sick	n/N (%)	n/N (%)
p (between groups)		

Table 9. Results of the assessment of the incidence of COVID-19 at the end of the prevention period (ITT population, PP)

	GROUP I	GROUP II
Total subjects	N =	N =

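### Only the control diary asks about medicines taken to prevent ARVI, so on-study use is ascertained unequally, with the weaker prompt in the arm where it is prohibited

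*Protocol*

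**What the plan says.** The arms have different rules on other preventive medicines (Protocol, Prohibited therapy). In Group I, "For the study group: use of any medications that may or may have preventive effects against ARVI, including COVID-19, is" prohibited. In Group II, interferon gamma is prohibited, but "use of any medications that may or may have preventive effects against ARVI, including COVID-19, as well as the use of non-specific methods" of protection is not. The section closes with a recording rule that names no arm: "All preventive measures, including pharmacotherapeutic ones, should be indicated in the diary filled in by the participant". Item 1 of the Protocol's exclusion criteria is "The use of the prohibited therapy indicated above, specific to each of the groups".

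The two diaries differ. Appendix 2 (control group) gives an observation period of 2 months and asks: "If you are taking medications to prevent ARVI, please fill out the table below". A separate prompt for complaints follows. Appendix 1 (study group) has a field for the time of administration on dose days, and each day page carries "In case of complaints, symptoms of ARVI, please fill out the table below" above a table headed "Start date | End date | Complaints | Therapy (if taken").

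The SAP (5.1, Analysis of the source data) says that medications used will be described by treatment group. Its table shells (Section 6) include "Table 6. Methods of nonspecific prevention (safety population"), which lists masks, respirators, gloves, glasses and overalls, and Table 24 on COVID-19 vaccination status. No shell covers ARVI-preventive medicines.

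**The concern.** A Group I participant without symptoms who takes another preventive product has no field in which to record it. The only drug column in that diary belongs to a complaint. The Protocol's recording rule therefore cannot be met with the form supplied to that arm, while the other arm has a dedicated table.

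The gap lies in the arm where the information decides more. In Group I, use of any other ARVI-preventive medicine is a reason for exclusion. In Group II, most such use is allowed and has no consequence for the participant's status. The form asks where the answer is mostly harmless and does not ask where it leads to exclusion.

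Three things depend on this information: who is excluded under criterion 1, who stays in the per-protocol set, and what the report can say about medications used in each arm. The SAP (5.5) uses the per-protocol set to test the sensitivity of the ITT result, so undetected users would remain in a set meant to be free of significant deviations. In an open-label trial that allows co-prophylaxis in one arm and forbids it in the other, readers will want to know how much was actually used on each side.

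**Working it through.** The point rests on no figure in the plan, so the check compares the texts and makes one count.

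**1. On-study capture of ARVI-preventive medicines, by arm**

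| Source | Group I | Group II |
|---|---|---|
| Rule on use (Prohibited therapy) | Prohibited | Allowed, except interferon gamma |
| Rule on recording (same section) | Required in diary | Required in diary |
| Diary prompt for preventive medicines | None in Appendix 1 | Dedicated prompt and table in Appendix 2 |
| Diary period shown | Course days only | 2 months |
| Visit 2 (phone) | Exclusion criteria checked | Exclusion criteria checked |
| Visit 3 | Exclusion check not marked | Exclusion check not marked |

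The Visit 0 anamnesis records vaccination status and means of prevention in both arms, but only at baseline.

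**2. Coverage of the Group I diary**

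- Day pages shown: Course 1 Days 1 to 9 and Course 2 Days 1 to 9, so 9 + 9 = 18.
- Preventive course: 10 + 7 + 10 = 27 days. Days without a page: 27 − 18 = 9, namely the 7-day break and Day 10 of each course.
- Planned participation: 56 to 62 days. Days without a page: 56 − 18 = 38 to 62 − 18 = 44.
- Day pages that ask about preventive medicines: 0 of 18.

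**3. What the Visit 2 check can supply**

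Criterion 1 refers to the therapy prohibited in each group. At Visit 2 it therefore covers any other ARVI-preventive medicine in Group I, but only interferon gamma in Group II. It is one recalled answer, by phone, at the end of the course, and the documents give no scripted question. It can find some Group I users up to that day. It does not ask the two arms the same thing, and it does not reach the follow-up period.

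**4. Where the data are used**

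- Exclusion criterion 1 and the per-protocol set (SAP 5.5): directly.
- Description of medications used by arm (SAP 5.1): directly, with on-study data prompted by diary in one arm only.
- Primary test (SAP 5.1): an unadjusted comparison of proportions in the ITT population, regardless of compliance. It takes no input from these data.

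No size in participants or percentage points is given. The documents state neither how many participants would use such medicines nor how completely they would report them.

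**The case against.** The strongest reply is that the diary is not the only source. Exclusion criteria are checked in both arms at Visit 2, the Visit 0 anamnesis covers prevention and vaccination in both arms, and the Protocol also draws effectiveness data from primary medical documentation. This stands in part: prohibited use in Group I is not wholly unprompted. But the anamnesis is a baseline record, the Visit 2 check is a single recall, and neither equals a prospective table in the other arm.

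A second reply is that Appendix 1 may be incomplete in the copy read. Some figures are missing there, and the column headings of the Group II prevention table are also lost. This stands as a caveat. The day pages that can be read repeat one layout, and none has the prompt.

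A reader might also infer more than the documents support:

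- *That background prevention cannot be compared between arms.* Table 6 compares nonspecific measures by arm and Table 24 compares COVID-19 vaccination status. What lacks an equal basis is on-study use of ARVI-preventive medicines.
- *That vaccination is captured unequally.* Neither readable diary has a vaccination field, the Group II prompt asks about medications and names no vaccine, and baseline vaccination status is taken in both arms.
- *That a drug effect cannot be separated from co-medication because of the diary.* A missing field does not change what participants take. The possible confounding comes from the open-label design and the different rules by arm; a better diary would document it, not remove it.

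**Conclusion.** The point holds as an inconsistency between the Protocol's recording rule and the form given to Group I. On-study use of ARVI-preventive medicines is ascertained by a 2-month diary table in Group II, and in Group I by no diary prompt and one exclusion check by phone at Visit 2.

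Its reach is limited. It affects exclusions under criterion 1, per-protocol membership and the by-arm description of medications used. It leaves the ITT primary test as it is, and limits how that result can be interpreted. It should be corrected, but it does not by itself undermine the primary analysis.

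The conclusion assumes that the readable text of Appendix 1 shows the diary's full content. If the original has a preventive-medicine page or follow-up pages that were lost in the copy, the point falls or narrows accordingly.

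**What to change.** 1. Put the same table of ARVI-preventive medicines in both diaries, covering the full observation period, including the 7-day break and the time after Course 2 in Group I.
2. Ask the same question about such medicines in both arms at the Visit 2 call and at Visit 3.
3. Add a descriptive table to SAP Section 6, beside Tables 6 and 24: on-study ARVI-preventive medicines by arm, ITT population, to day 28 and to the end of the study.

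The cost is a little more paperwork for participants, one question at two contacts that already exist, and one more table. No rule on permitted or prohibited treatment changes. If the diaries have already been used as shown, the report should state that these medicines were prompted differently in the two arms wherever it describes medications used or per-protocol results.

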ATC – Anatomical Therapeutic Chemical Classification System
VI – viral infections
CI – confidence interval
IU – international unit
BMI – body mass index
INN – international nonproprietary name
IEC – Independent Ethics Committee
AE – adverse event
ARVI – acute respiratory viral infection
ARD – acute respiratory disease
SAR – serious adverse reaction
SARS – severe acute respiratory syndrome
COVID-19 – coronavirus disease 2019 (coronavirus disease 2019)
CTCAE – Toxicity Scale (Common Terminology Criteria for Adverse Events)
SARS-CoV-2 – type 2 coronavirus that causes severe acute respiratory syndrome (SARS)
M – arithmetic mean
Max – Maximum value
Me – Median
Min – minimum value
N – number of values
SD – standard deviation
ATC – Anatomical Therapeutic Chemical Classification System
VI – viral infections
CI – confidence interval
IU – international unit
BMI – body mass index
INN – international nonproprietary name
IEC – Independent Ethics Committee
AE – adverse event
ARVI – acute respiratory viral infection
ARD – acute respiratory disease
SAR – serious adverse reaction
SARS – severe acute respiratory syndrome
COVID-19 – coronavirus disease 2019 (coronavirus disease 2019)
CTCAE – Toxicity Scale (Common Terminology Criteria for Adverse Events)
SARS-CoV-2 – type 2 coronavirus that causes severe acute respiratory syndrome (SARS)
M – arithmetic mean

1. PURPOSES AND OBJECTIVES

1.1. Purpose of the study

Evaluation of the efficacy and safety of the prophylactic use of Ingaron (INN: human recombinant interferon gamma, lyophilizate for the preparation of a solution for intranasal administration of 100 000 IU) in the mode of 3 drops in each nasal passage intranasally every other day for 10 days with a break of 7 days (two 10-day cycles) in adult volunteers.

1.2. Research objectives

Evaluation of the effectiveness and safety of the proposed regimen of preventive therapy with Ingaron (INN: human recombinant interferon gamma, lyophilizate for the preparation of a solution for intranasal administration of 100 000 IU) in adult volunteers.

2. CLINICAL TRIAL DESIGN

2.1. Design

Post-marketing non-interventional prospective randomized open-label comparative study.

A total of 4 visits are planned (0–3). Visit 0 and 1 can be combined.

During randomization, participants are randomly distributed in a 1:1 ratio into two groups:

[figure not shown]
Group I (main) and Group II (control).

According to the methodology approved by this protocol, the participant must use (Group I) or not use (Group II) study drug (depending on the distributed randomization number at Visit 1) for 27 days of the preventive course (10 days + 7 days + 10 days).

The effectiveness of preventive therapy will be recorded. The presence and severity of any adverse events and events will also be evaluated, regardless of the alleged connection with the use of the study drug Ingaron®.

The schedule of visits and procedures is identical for all study participants. A detailed description of the research procedures is provided in the Protocol.

The schedule of research procedures is presented in the section DESIGN of NON-INTERVENTIONAL RESEARCH Protocol. The study periods with the planned time are shown in the diagram below:

Scheme 1. Design

